### **9.4 Blood products and growth factors**

Blood products and growth factors should be utilized as clinically warranted and following institutional policies and recommendations. The use of growth factors should follow published guidelines of the Journal of Clinical Oncology, Vol 24, No 18 (June 20), 2006: pp. 2932-2947.

**Interference with Serological Testing:** Daratumumab binds to CD38 on red blood cells (RBCs) and results in a positive Indirect Antiglobulin Test (Coombs test). Daratumumab-mediated positive indirect antiglobulin test may persist for up to 6 months after the last daratumumab infusion. Daratumumab bound to RBCs masks detection of antibodies to minor antigens in the patient's serum. The determination of a patient's ABO and Rh blood type are not impacted. Notify blood transfusion centers of this interference with serological testing and inform blood banks that a patient has received Daratumumab. Type and screen patients prior to starting Daratumumab.

### **9.5 Diarrhea**

Diarrhea should be managed according to clinical practice, including the administration of antidiarrheals such as loperamide once infectious causes are excluded. Fluid intake should be maintained to avoid dehydration. Fluid deficit should be corrected before

initiation of treatment and during treatment. Additional doses of loperamide at 2 mg every 2-4 hours until diarrhea free (maximum 16 mg/day).

In the event of Grade 3 or 4 diarrhea, the following supportive measures are allowed: hydration, octreotide, and antidiarrheals.

If diarrhea is severe (requiring intravenous rehydration) and/or associated with fever or severe neutropenia (Grade 3 or 4), broad-spectrum antibiotics must be prescribed.

Patients with severe diarrhea or any diarrhea associated with severe nausea or vomiting **should be hospitalized** for intravenous hydration and correction of electrolyte imbalances.

Please monitor patients carefully for development of ileus.

#### 9.6 Renal failure and Ixazomib

Two cases of acute renal failure have been reported in patients treated at or above the MTD for intravenous ixazomib (see Section 1.4.3). Volume depletion should be corrected before initiation of study drug. Until further information is available, intake of nonsteroidal anti-inflammatory drugs immediately prior to the administration of ixazomib should be discouraged and requires consultation with the principal investigator. All necessary supportive care consistent with optimal patient care shall be available to patients as necessary.

#### 9.7 Herpes Zoster prophylaxis

Patients may be at an increased risk of infection including reactivation of herpes zoster and herpes simplex viruses. Prophylaxis with acyclovir 400 mg PO BID is should be used while on study therapy and for 3 months beyond the end of therapy.

#### 9.8 Prohibited medications

##### 9.81 Prohibited enzyme inducers

Systemic treatment with any of the following metabolizing enzyme inducers should be avoided, unless there is no appropriate alternative medication for the patient's use. (Rationale: If there were to be a drug-drug interaction with an inducer, ixazomib exposure would be decreased)

Strong CYP3A inducers: rifampin, rifapentine, rifabutin, carbamazepine, phenytoin, and phenobarbital.

##### 9.82 Excluded foods and dietary supplements include St. John's wort.

#### 9.9a Erythematous Rash with or without Pruritus

Rash with or without pruritus has been reported with ixazomib, primarily at the higher doses tested and when given with agents where rash is an overlapping toxicity. The rash may range from limited erythematous areas, macular and/or small papular bumps that may or may not be pruritic over a few areas of the body, to a more generalized eruption that is predominately on the trunk or extremities. Rash has been most commonly characterized as maculopapular or macular. To date, when it does occur, rash is most commonly reported within the first 3 cycles of therapy. The rash is often transient, self-

limiting, and is typically Grade 1 to 2 in severity. Rash can also be seen with lenalidomide, and usually responds to dose interruption and dose decrease.

Symptomatic measures such as antihistamines or corticosteroids (oral or topical) have been successfully used to manage rash and have been used prophylactically in subsequent cycles. The use of a topical, IV, or oral steroid (e.g., prednisone  $\leq 10$  mg per day or equivalent) is permitted. Management of a Grade 3 rash may require intravenous antihistamines or corticosteroids. Administration of ixazomib (and/or other causative agent if given in combination) should be modified per protocol and re-initiated at a reduced level from where rash was noted (also, per protocol).

In line with clinical practice, dermatology consult and biopsy of Grade 3 or higher rash or any SAE involving rash is recommended. Prophylactic measures should also be considered if a patient has previously developed a rash (e.g., using a thick, alcohol-free emollient cream on dry areas of the body or oral or topical antihistamines). A rare risk is Stevens-Johnson Syndrome, a severe and potentially life-threatening rash with skin peeling and mouth sores, which should be managed symptomatically according to standard medical practice. Punch biopsies for histopathological analysis are encouraged at the discretion of the investigator.

#### 9.9b Thrombocytopenia

Blood counts should be monitored regularly as outlined in the protocol with additional testing obtained according to standard clinical practice. Thrombocytopenia may be severe but has been manageable with platelet transfusions according to standard clinical practice. Ixazomib and lenalidomide administration should be modified as noted as per dose modification recommendations in the protocol when thrombocytopenia occurs (see Section 8). Therapy can be reinitiated at a reduced level upon recovery of platelet counts. A rare risk is thrombotic thrombocytopenic purpura (TTP), a rare blood disorder where blood clots form in small blood vessels throughout the body characterized by thrombocytopenia, petechiae, fever, or possibly more serious signs and symptoms. TTP should be managed symptomatically according to standard medical practice.

#### 9.9c Neutropenia

Blood counts should be monitored regularly as outlined in the protocol with additional testing obtained according to standard clinical practice. Neutropenia may be severe but has been manageable. Growth factor support is not required but may be considered according to standard clinical practice. Ixazomib administration should be modified as noted as per dose modification recommendations in the protocol when neutropenia occurs (see Section 8). Therapy can be reinitiated at a reduced level upon recovery of ANCs.

#### 9.9d Fluid Deficit

Vitals should be assessed prior to start of each cycle as per Table 4.1. Dehydration should be avoided since ixazomib may cause vomiting, diarrhea, and dehydration. Patients should be encouraged to maintain adequate fluid intake. Acute renal failure has been reported in patients treated with ixazomib, commonly in the setting of the previously

noted gastrointestinal toxicities and dehydration. Fluid deficit should be corrected before initiation of study drug and as needed during treatment to avoid dehydration.

9.9e Hypotension

Symptomatic hypotension and orthostatic hypotension with or without syncope have been reported with ixazomib. Blood pressure should be closely monitored while the patient is on study treatment and fluid deficit should be corrected as needed, especially in the setting of concomitant symptoms such as nausea, vomiting, diarrhea, or anorexia. Patients taking medications and/or diuretics to manage their blood pressure (for either hypo- or hypertension) should be managed according to standard clinical practice, including considerations for dose adjustments of their concomitant medications during the course of the trial. Fluid deficit should be corrected before initiation of study drug and as needed during treatment to avoid dehydration.

9.9f Posterior Reversible Encephalopathy Syndrome

One case of posterior reversible encephalopathy syndrome, which ultimately resolved, has been reported with ixazomib. This condition is characterized by headache, seizures and visual loss, as well as abrupt increase in blood pressure. Diagnosis may be confirmed by magnetic resonance imaging (MRI). If the syndrome is diagnosed or suspected, symptom-directed treatment should be maintained until the condition is reversed by control of hypertension or other instigating factors.

9.9g Transverse Myelitis

Transverse myelitis has also been reported with ixazomib. It is not known if ixazomib causes transverse myelitis; however, because it happened to a patient receiving ixazomib, the possibility that ixazomib may have contributed to transverse myelitis cannot be excluded.

9.9h Guidelines for Prevention of Infusion Reactions

Pre-infusion Medication: On daratumumab infusion days, subjects will receive the following medications prior to infusion:

- Acetaminophen (paracetamol) 650-1000 mg IV or orally (PO) approximately 1 hour or less prior to daratumumab infusion
- An antihistamine (diphenhydramine 25-50 mg IV or PO, or equivalent) approximately 1 hour (or less) prior to infusion
- Dexamethasone 40 mg IV or PO (only if IV is not available), approximately 1 hour or less prior to daratumumab infusion. On days when subjects receive this dose of dexamethasone in the clinic, dexamethasone will not be self-administered at home.

Post-infusion Medication: For subjects with higher risk of respiratory complications (ie, subjects who have a FEV1 <80%), the following postinfusion medications should be considered:

- Antihistamine (diphenhydramine or equivalent)

- Dexamethasone 4 mg day after infusion
- Short-acting  $\beta$ 2 adrenergic receptor agonist such as salbutamol aerosol
- Control medications for lung disease (eg, inhaled corticosteroids  $\pm$  long-acting  $\beta$ 2 adrenergic receptor agonists for subjects with asthma; long-acting bronchodilators such as tiotropium or salbutamol  $\pm$  inhaled corticosteroids for subjects with COPD)

In addition, these at-risk subjects may be hospitalized for monitoring for up to 2 nights after an infusion. If subjects are hospitalized, then their FEV1 should be measured before discharge. If these subjects are not hospitalized, then a follow up telephone call should be made to monitor their condition within 48 hours after all infusions. If the subject has not experienced a significant medical event but is hospitalized overnight only for observation, then the hospitalization should not be reported as a serious adverse event. Investigators may prescribe bronchodilators, antihistamines, and corticosteroids that are deemed necessary to provide adequate supportive care in the event a bronchospasm occurs after subjects are released from the hospital/clinic.

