### 7.1 Treatment Schedule Arm A

Table 7.1			
Induction phase (Cycles 1-12)			
Drug	Route	Dose	Schedule Each cycle is 28 days
Ixazomib	Oral	4 mg	Days 1, 8 and 15
Lenalidomide	Oral	25 mg (if CrCl >60 ml/min)	Days 1-21
		10 mg (if CrCl 30-60 ml/min)	
Daratumumab	IV	16 mg/kg	Cycles 1 and 2: Days 1, 8, 15, 22
			Cycles 3, 4, 5, and 6: Days 1, 15
			Cycles 7 and beyond: Day 1
Dexamethasone	IV/ Oral*	40 mg	Days 1, 8, 15 and 22 Arm A: Cycles 1-12
* On days when daratumumab is given, dexamethasone is given IV over 15 minutes within 1 hour prior to daratumumab			
Maintenance Phase (Cycle 13 + up to 36 months from registration)			
Ixazomib	Oral	4 mg	Days 1, 8 and 15
Daratumumab	IV	16 mg/kg	Day 1
Cycle = 28 days			

NOTE: Once the creatinine clearance is >60 mL/min during the course of the treatment, lenalidomide can be increased to 25 mg.

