### Treatment Schedule Arm B

Table 7.1			
Induction phase (Cycles 1-12)			
Drug	Route	Dose	Schedule Each cycle is 28 days
Ixazomib	Oral	4 mg	Days 1, 8 and 15
Lenalidomide	Oral	25 mg (if CrCl >60 ml/min)	Days 1-21
		10 mg (if CrCl 30-60 ml/min)	
Daratumumab	IV	16 mg/kg	Cycles 1 and 2: Days 1, 8, 15, 22
			Cycles 3, 4, 5, and 6: Days 1, 15
			Cycles 7 and beyond: Day 1
Dexamethasone	IV/ Oral*	40 mg	Days 1, 8, 15 and 22 Arm B: Cycles 1-2
* On days when daratumumab is given, Dexamethasone is given IV over 15 minutes within 1 hour prior to daratumumab			
Maintenance Phase (Cycle 13 + up to 36 months from registration)			
Ixazomib	Oral	4 mg	Days 1, 8 and 15
Daratumumab	IV	16 mg/kg	Day 1
Cycle = 28 days			

NOTE: Once the creatinine clearance is >60 mL/min during the course of the treatment, lenalidomide can be increased to 25 mg.

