**ALERT: ADR reporting may be required for some adverse events (See Section 10)**

8.1 Dose Levels for each drug in the combination  
 (Based on Adverse Events in Tables 8.2-5)

**NOTE:** Toxicities attributable to dexamethasone should lead to dose reduction only for dexamethasone.

Table 8.1 Dose reduction steps				
Step	Ixazomib	Lenalidomide	Daratumumab	Dexamethasone
0	4 mg	25 mg	NA	40 mg
-1	3 mg	15 mg		24 mg
-2	2.3 mg	10 mg		12 mg
-3	Discontinue	5 mg		4 mg
-4	Discontinue	Discontinue		Discontinue

8.11 Instruction for initiation of a new cycle of therapy or restarting therapy after interruption during a cycle for toxicities

A new cycle of treatment may begin on the scheduled Day 1 of a new cycle if:

- The ANC is  $\geq 1000/\mu\text{L}$
- The platelet count is  $\geq 75,000/\mu\text{L}$
- Any other non-hematologic treatment -related adverse event that may have occurred has resolved to  $\leq$ Grade 1 or baseline severity.

If these conditions are not met on Day 1 of a new cycle, the subject will be evaluated weekly and a new cycle of therapy will be held until the toxicity has resolved as described above.

If any drug dosing was halted during the previous cycle and was restarted with a one-level dose reduction without requiring an interruption for the remainder of the cycle, then that reduced dose level will be initiated on Day 1 of the new cycle.

If any drug dosing was omitted for the remainder of the previous cycle or if the new cycle is held due to known hematologic toxicity newly encountered on the scheduled Day 1, then the new cycle will be started with a one-level dose reduction. If a new cycle of therapy cannot be restarted within 4 weeks of the scheduled Day 1 due to non-resolution of drug related toxicities, the patient will be removed from protocol therapy and will go to event monitoring.

→ → Use the NCI Common Terminology Criteria for Adverse Events (CTCAE) version 4.0\* unless otherwise specified ← ←

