## 8.4 Dose modifications for dexamethasone (Dex) based on adverse events during a cycle

CTCAE System/Organ/Class (SOC)*	ADVERSE EVENT	ACTION**
Gastrointestinal disorders	Dyspepsia, gastric or duodenal ulcer, gastritis Grade 1-2 (Symptomatic; altered GI function; medical intervention indicated; limiting instrumental ADL)	Treat with H2 blockers, sucralfate, or omeprazole If symptoms persist despite above measures, decrease dexamethasone dose by 1 dose level
	Dyspepsia, gastric or duodenal ulcer, gastritis $\geq$ Grade 3 (Severely altered GI function; TPN indicated; elective operative or endoscopic intervention indicated; limiting self-care ADL; disabling)	Omit dexamethasone until symptoms adequately controlled Restart one dose level below along with concurrent therapy with H2 blockers, sucralfate, or omeprazole If symptoms persist despite above measures, discontinue dexamethasone and do not resume.
Gastrointestinal disorders	Pancreatitis $\geq$ Grade 3 (Severe pain; vomiting; medical intervention indicated (e.g., analgesia, nutritional support))	Discontinue dexamethasone and do not resume
General disorders and administration site conditions	Edema $\geq$ Grade 3 (limiting function and unresponsive to therapy or anasarca)	Diuretics as needed, and decrease dexamethasone dose by 1 dose level If edema persists despite above measures, decrease dose another dose level Discontinue dexamethasone and do not resume if symptoms persist despite second reduction
Psychiatric disorders	Confusion or Mood alteration $\geq$ Grade 2 (Severe disorientation; limiting self-care ADL)	Omit dexamethasone until symptoms resolve Restart with one dose level reduction If symptoms persist despite above measures, discontinue dexamethasone and do not resume
Musculoskeletal and connective tissue disorders	Muscle weakness $\geq$ Grade 2 Weakness limiting self-care ADL; disabling	Decrease dexamethasone dose by one dose level; if weakness persists despite above measures decrease dose by one additional dose level Discontinue dexamethasone and do not resume if symptoms continue to persist
Metabolism and nutrition disorders	Hyperglycemia Grade 3 or higher ( $>250 - 500$ mg/dL; $>13.9 - 27.8$ mmol/L); hospitalization indicated	Treatment with insulin or oral hypoglycemics as needed If uncontrolled despite above measures, decrease dose by one dose level at a time until levels are satisfactory

\* Located at [REDACTED]

\*\* Use the following to describe actions in the Action column:

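### Sections 7.1, 7.5, 8.1, 8.4 and 9.9h give conflicting instructions on dexamethasone before daratumumab once dexamethasone has been reduced or stopped for toxicity, and nothing says which governs

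*Combined protocol and SAP*

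**What the plan says.** **Premedication (Section 9.9h).** The list opens "On daratumumab infusion days, subjects will receive the following medications prior to infusion" and includes "Dexamethasone 40 mg IV or PO (only if IV is not available), approximately 1 hour or less prior to daratumumab infusion". No exception is made by arm, cycle or dose level, and Section 8 is not mentioned. The section adds: "On days when subjects receive this dose of dexamethasone in the clinic, dexamethasone will not be self-administered at home".

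**Schedule (Section 7.1).** The Arm A table carries the footnote "On days when daratumumab is given, dexamethasone is given IV over 15 minutes within 1 hour prior to daratumumab". The Arm B table carries the same one: "On days when daratumumab is given, Dexamethasone is given IV over 15 minutes within 1 hour prior to daratumumab".

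**Toxicity rules (Section 8).** Table 8.1 sets the steps 40, 24, 12 and 4 mg, then discontinuation, with the note "Toxicities attributable to dexamethasone should lead to dose reduction only for dexamethasone". Section 8.4 orders reductions for several toxicities. For severe upper-GI events and for mood or confusion events it ends with "If symptoms persist despite above measures, discontinue dexamethasone and do not resume". It orders the same permanent stop outright for pancreatitis of Grade 3 or higher, and for edema or muscle weakness that persists after two reductions. The introduction to Section 8.0 makes the modifications strict for the first two cycles and guidance thereafter.

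**Early stopping (Section 7.5).** Arm A may stop dexamethasone early for toxicity; premedication is not mentioned. Arm B stops after two cycles, or earlier for toxicity, and dexamethasone given as infusion prophylaxis is then allowed to go on, with no dose stated. For dexamethasone dose reductions this section refers to Section 8.2, which is the ixazomib table.

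**The concern.** A patient reduced to 12 mg, or stopped for pancreatitis, who attends for the next daratumumab infusion is covered by two instructions that cannot both be followed. Under 9.9h the dose is 40 mg. Under 8.1 and 8.4 it is 12 mg, or none. The situation is foreseeable: the Table 8.1 note confines the response to dexamethasone toxicity to dexamethasone itself, so daratumumab would ordinarily continue.

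Two things are at stake. One is safety: depending on the section a site reads, the patient either receives the full dose again after a steroid toxicity or is infused with less steroid cover or none. The other is interpretation: delivered dexamethasone and the steroid-related adverse event tables would partly reflect each site's reading. That matters in a study whose stated reason for Arm B is to lower steroid exposure.

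**Working it through.** The plan states no figure on this point, so there is none to reproduce. The check has two parts: whether the texts govern the same dose, and how many doses are affected.

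**1. Same dose or two doses?** The Section 7.1 footnotes place the scheduled dexamethasone within the hour before daratumumab. Section 9.9h removes the home dose on those days. There is therefore one administration, with the treatment rules of Section 8 and the prophylaxis rule of 9.9h both applying to it.

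**2. Overlap of days.** Inputs are from the Section 7.1 tables. Dexamethasone is scheduled on Days 1, 8, 15 and 22 (Arm A Cycles 1-12, Arm B Cycles 1-2). Daratumumab is given on Days 1, 8, 15 and 22 in Cycles 1-2, Days 1 and 15 in Cycles 3-6, and Day 1 from Cycle 7.

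| Cycles | Scheduled dexamethasone days | Of these, infusion days |
|---|---|---|
| 1-2 (both arms) | 2 × 4 = 8 | 2 × 4 = 8 |
| 3-6 (Arm A) | 4 × 4 = 16 | 4 × 2 = 8 |
| 7-12 (Arm A) | 6 × 4 = 24 | 6 × 1 = 6 |
| Arm A total | 48 | 22 |

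In Arm A, 22/48 = 46% of scheduled doses fall on infusion days, leaving 48 − 22 = 26 that do not. In Arm B it is 8/8 = 100%. Arm B has a further 22 − 8 = 14 infusions in Cycles 3-12, after scheduled dexamethasone has ended.

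**3. Size per patient (illustrative).** Let d be the reduced dose and n the number of infusion days in a cycle. If Table 8.1 governs every day, the cycle total is 4d. If 9.9h governs infusion days, it is 40n + (4 − n)d. At d = 12 mg:

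- Cycle 2, n = 4: 4 × 12 = 48 mg against 4 × 40 = 160 mg (3.3-fold).
- Arm A, each of Cycles 3-6, n = 2: 48 mg against 2 × 40 + 2 × 12 = 104 mg (2.2-fold).
- Arm A, each of Cycles 7-12, n = 1: 48 mg against 40 + 3 × 12 = 76 mg (1.6-fold).

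The first comparison is given for Cycle 2 only. Reductions follow adverse events seen after earlier dosing and 12 mg is the second step, so no patient can be at 12 mg throughout Cycle 1. After a permanent stop in Arm A, the literal readings are 0 mg and 40 mg at each remaining infusion.

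**4. Does any text settle it?**

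| Situation | Section 9.9h | Section 8 | Section 7.5 |
|---|---|---|---|
| Reduced dose, either arm | 40 mg | 24, 12 or 4 mg | No statement on the pre-infusion dose |
| Toxicity stop, Arm A | 40 mg | None, not to be resumed | Silent on premedication |
| Toxicity stop, Arm B | 40 mg | None, not to be resumed | Prophylaxis permitted, dose not given |

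No row is resolved. In the last, the permissive wording of 7.5 differs from both the mandatory wording of 9.9h and the stop in 8.4.

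**The case against.** The best defence is that the 40 mg in 9.9h is simply the starting dose. Table 7.1 also states 40 mg without a proviso for reduced patients, and nobody takes that to disable Table 8.1. If the infusion-day dose is the treatment dose, Section 8 should modify it. Section 7.0 sends toxicity modifications to Section 8, Section 8.0 is strict in exactly the two cycles where every dexamethasone day is an infusion day, and 9.9h is headed as guidelines. After Cycle 2 Section 8 becomes guidance too, so the clash is then less absolute. For Arm B, Section 7.5 does address prophylaxis after a stop.

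Much of this stands. A reader might infer that the reduction table has no effect on infusion days in either arm. The documents do not support that, because it requires 9.9h to override Section 8 and no text says so.

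The defence does not remove the conflict. Section 9.9h is worded as mandatory, offers no alternative dose and does not point to Section 8. The Arm B sentence in 7.5 treats prophylactic dexamethasone as something that can outlast treatment dexamethasone, which sits badly with the view that the Section 8 steps simply carry over to it. For Arm A after a toxicity stop, no section speaks to the question.

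A reader might also infer that infusion-reaction rates will differ by site. That is not shown. Section 1.5 reports these reactions mostly in the first cycle, and Section 15.49 places severe ones usually at the first infusion, which no toxicity reduction can precede.

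**Conclusion.** The conflict is real and unresolved. After a toxicity reduction or stop, Sections 7.1, 7.5, 8.1, 8.4 and 9.9h do not yield one infusion-day dexamethasone instruction. The counts of 8 of 8 doses in Cycles 1-2 and 22 of 48 in Arm A follow from the schedule alone. That a reduction would leave those doses unchanged depends on reading 9.9h literally. The milligram comparisons also assume a patient who stays at the 12 mg step for the whole cycle and receives every scheduled dose.

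The point concerns only patients with dexamethasone toxicity who remain on daratumumab. The documents give no figure for how many that will be. Sample size, alpha, power and the definition of the primary endpoint are untouched. It still warrants correction, because incompatible instructions apply to patients already harmed by the drug, in both arms, from as early as Cycle 1 once a toxicity has occurred. This review takes no view on which dose or rule is right.

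**What to change.** Amend Sections 7.1 (footnotes), 7.5, 8.1, 8.4 and 9.9h so that they state one rule, for each arm, on:

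- whether the Table 8.1 steps apply to the pre-infusion dose;
- whether the Section 8.4 permanent stops apply to it, and so what a patient receives before daratumumab after permanent discontinuation;
- for Arm B, whether prophylactic dexamethasone is required or optional after a stop, and at what dose.

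Add cross-references between 9.9h and 8.4, and correct the reference in 7.5 that leads to the ixazomib table. The sponsor decides the clinical content.

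The cost is a few sentences in an amendment. Section 7.5 already requires accurate records of all drug administration, so delivered pre-infusion dexamethasone should be available for the exposure summary without new data collection. No sample size or analysis change is needed.
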